10.8 Electronic medical record data

The following data from the participants' EMR *Sundhedsplatformen* will be collected at V1 by the investigator. Changes in glucose- and cholesterol-lowering medications and changes in other medications e.g. diuretics throughout the study will be registered after visits V5 and V6 and total number of visits at a diabetologist and diabetes nurse during the study period will be registered at V6.

- Type of diabetes
- Gender
- Date of birth
- Smoking status
- Diabetes duration
- Gastroparesis
- Prescribed insulin, types and dosages
- Prescribed oral antidiabetics, types and dosages
- Prescribed cholesterol lowering medication, types and dosages
- Prescribed other medication and dose or changes in dose of other medication
- Previous participation in a BCC group program
- Use of open CGM
- Use of a Freestyle Libre
- Use of an automated bolus calculator

10.9 Other baseline demographics

The following self-administered questions on baseline demographics will be sent out electronically before V1 using the software system REDCap (appendix 13).

[figure not shown]
- Educational level
- Main occupation
- Civil status and household composition
- Yearly income

10.10 Physical activity level

Physical activity level will be assessed using IPAQ SF (appendix 12). Participants will be encouraged to continue their habitual level of physical activity and not to change it during the 24 weeks study period. IPAQ SF will be send electronically before visits V1, V5 and V6.

11 Study visits

The following section describes all visits included in the study. The visits are also schematically presented in table 1. The visits will be conducted by the principle study investigator and study personnel under responsibility of the principle investigator. Examinations are described in section 10. For logistical reasons, windows are allowed for the study visits (\pm 21 days). A detailed visit flow for all three groups is presented in **Figure 2**.

ABC-ACC; automated bolus calculation combined with advanced carbohydrate counting; BCC=basic Carbohydrate counting; BP= blood pressure; BW=body weight; CGM=continuous glucose monitoring; DXA=dual-energy-X-ray absorptiometry; V=visit.

Figure 2 Visit flow

11.1 Study information

The following procedures will be performed in the following order:

- Short oral information by phone
- Written patient information
- Personal meeting for thorough oral information
- Invitation to participate in the study after the patient has had time for reflection (at least 24 hours)

11.2 Screening

- A signed informed written consent has been collected before continuing
- A non-fasting blood sample for assessment of HbA1c (screening criteria)
- Screening for study eligibility according to inclusion and exclusion criteria,
- If not eligible for inclusion the cause of screening failure is recorded and explained to the patient
- Participants eligible for inclusion will be registered with an ID code
- Randomization will be performed before the participant is sent home

11.3 V1: Baseline (week -4 to -1)

At visit 1 the following procedures and assessments will be performed in the morning after 8-10 hours fast:

- Collection of fasting blood samples
- Measurement of height, body weight, blood pressure, hip and waist circumference (fasting condition)
- Pregnancy test (woman only)
- Full body DXA scan (fasting condition)
- A meal is provided for the participant
- Fill in questionnaire concerning demographic data, CPQ, Mathematical literacy test, DDRQOL, PCS, HCCQ, IPAQ SF at V1
- Collection of medical history including registration of glucose- and lipid-lowering medicine
- Instruction in how to fill out the three days of dietary registration forms
- Instruction in how to collect four days of urine sample and how to hand in the sample
- Injection of CGM device and instruction in precautions and how to hand in the CGM
- Instruction in recording four daily PG measurements in six days with CGM

11.4 V2: Start of intervention, day 1 (week 0)

At visit 2 the following procedures and assessments will be performed:

- Update of glucose- and lipid-lowering medicine
- BCC/ABC-ACC: group-based education activities according to curriculum delivered by two dietitians
- Control: initial individual dietary counselling by a dietitian

11.5 V3: Intervention, day 2 (week 2)

At visit 3 the following procedures and assessments will be performed:

- Update of glucose- and lipid-lowering medicine
- BCC: group-based education activities according to curriculum delivered by two dietitians
- ABC-ACC: individual follow-up with a dietitian
- Control: individual dietary counselling follow-up by a dietitian

11.6 V4: Intervention, day 3 (week 12)

At visit 4 the following procedures and assessments will be performed:

- Collection of blood sample (non-fasting condition)
- Update of glucose- and lipid-lowering medicine
- Measurement of body weight (non-fasting condition)
- BCC: group-based education activities according to curriculum delivered by two dietitians
- ABC-ACC: individual follow-up with a dietitian
- Control: individual dietary counselling follow-up by a dietitian

11.7 V5: After 24 weeks of intervention

At visit 5 the following procedures will be performed in the morning after 8-10 hours fasting:

- Collection of fasting blood samples
- Measurement of body weight, blood pressure, hip and waist circumference (fasting condition)
- Check for pregnancy (women only)
- Full body DXA scan (fasting condition)
- A meal is provided for the participant
- Participants who has not filled in all questionnaires before V5 will be asked to fill in at V5
- Update of glucose- and lipid-lowering medicine
- Instruction in how to fill out the three days of dietary registration forms
- Instruction in how to collect four days of urine sample and how to hand in the sample
- Injection of CGM device and instruction in precautions and how to hand in the CGM
- Instruction in recording four daily PG measurements in six days with CGM

11.8 V6: Follow-up at 48 weeks (24 weeks after completing the intervention period)

At visit 6 the following procedures will be performed in the morning after 8-10 hours fasting:

- Collection of fasting blood samples
- Measurement of body weight, blood pressure, hip and waist circumference (fasting condition)
- Update of glucose- and lipid-lowering medicine
- Participants who has not filled in all questionnaires before V6 will be asked to fill in at V6
- A meal is provided for the participant

12 Laboratory Analyses

12.1 Laboratory

Laboratory analyses will be performed in the Department of Clinical Biochemistry at SDCC, [name].

The current and emerging biomarkers of total carbohydrate intake and of carbohydrate-rich foods have been developed by University of Copenhagen (Preventive and Clinical Nutrition group, Dept. of Nutrition, Exercise and Sports (NEXS)) and others using equipment available at SDCC (Systems Medicine Group).

12.2 Sample Handling

Blood samples will be drawn in the morning from all study participants as part of V1, V4, V5 and V6. Blood samples will be drawn and handed according to standard operational procedures (SOPs) specified by the Clinical Biochemical Department at SDCC which is responsible for the collection and analysis of the samples and storage locally until further data analysis. Blood samples in the study will be analysed immediately including plasma HbA1c at V1 in all potential participants since this measurement is used as part of the screening to assess if the patient is eligible for inclusion in the study. The total volume of blood drawn during the 48 weeks is a maximum of 182 ml, with 60 ml drawn at V1, V5 and V6 including 3 x 10 ml for a biobank for future research, as specified in **table 2**. Any remaining samples and left over will be destroyed after conducting the analysis and storing of 30 ml for the biobank for future research.

Table 2: Maximum volume of blood collected

Visit number	Week number	Max blood volume (ml)
Visit 1	-4 to -1	60
Visit 4	12	2
Visit 5	24	60
Visit 6	48	60

Urine will be collected as midstream urine spots four times daily (4 x 3 ml) for four days by the participants after V1 and V5 and will be analysed to estimate the albumin-creatinine ratio and metabolomics analysis for excretion of biomarkers related to carbohydrate intake (sucrose, fructose, mannose and lactose) and qualitative markers of common groups of carbohydrate rich foods including vegetables, fruit, whole grain, and possibly potato, beet root, and rice and other intermediate metabolites at SDCC. After the return of urine collections at SDCC, these will be handed according to specific SOPs and stored until further data analysis for determination of metabolic profile (metabolomics analysis) at SDCC. The total volume of urine collected during the 48 weeks is 96 ml, with 48 ml being collected at each of the two visits (including 12 ml at V1 and V5 for a biobank for future research), as specified in **table 3**.

Table 3: Maximum volume of urine collected

Visit number	Week number	Max urine volume (ml)
Visit 1	-4 to -1	48
Visit 5	24	48

The collected blood and urine samples will be used for the following analysis in the study listed in **Table 4**.

Table 4: Analysis of biochemical samples

Visit	Visit 1	Visit 4	Visit 5	Visit 6
Week	-4 to -1	12	24	48
P-ALAT	X		X	X
P-Albumin	X		X	X
U-Albumin	X		X	
P-Alkaline phosphatase	X		X	X
P-C-peptide	X			
P-Cobalamin	X		X	X
P-Creatinine	X		X	X
U-Creatinine	X		X	
P-HbA1c	X	X	X	X
P-HDL cholesterol	X		X	X
P-Haemoglobin	X		X	X
P-LDL cholesterol	X		X	X
P-Potassium	X		X	X
P-Sodium	X		X	X
P-Total cholesterol	X		X	X
P-Triglyceride	X		X	X
P-TSH	X		X	X
P-VLDL cholesterol	X		X	X
Metabolomics analysis (urine)	X		X	
Biobank - plasma	X		X	X
Biobank - urine	X		X	

ALAT = Alanine aminotransferase; HbA1c = Glycosylated haemoglobin; HDL = High-density-lipoprotein; LDL = Low-density-lipoprotein; TSH = Thyroid-stimulating hormone; VLDL = Very-low-density-lipoprotein.

12.3 Storage of samples

Urine samples in the study will be stored and analysed after the last patient's last visit in the study, while blood and urine samples specifically collected for the biobank for future research will be stored in -80 degrees freezer at SDCC, [name].

12.4 Samples for a research biobank and a biobank for future research

A research biobank will be established for some of the samples as specified in the current protocol. The aim of establishing the research biobank is to store urine samples from the participants for biochemical analysis after the last patient's last visit in the study. The samples will be kept until 31.12.2022 where the final analysis and study will be finished. At visits V1 and V5 urine samples of maximum 48 ml will be collected (96 ml in total during the study period) and stored in the research biobank. Any urine left in the research biobank after all relevant biochemical measurements have been performed will be destroyed.

In addition to the research biobank, a biobank with additional blood and urine samples from the participants for use in future research within the area of diabetes not specified in the present protocol will be established. The donation of the additional blood and urine samples for a future biobank is voluntary, and will not affect the participants further, as the blood is drawn together with the blood samples drawn as part of the study and urine spots are collected in the same days as urine is collected as part of the study. Hence it will not cause an additional burden on the patient. A total of 30 ml blood will be drawn (10 ml at V1, V5 and V6) and a total of 24 ml urine will be kept (12 ml at V1 and V5) and stored in freezer at SDCC, [name]. Donation of samples to the biobank for future research is voluntary, and the participants will be asked to sign an independent informed consent regarding donation of samples to the biobank for future

research. Rejection of donation of samples to the biobank, will not affect participation in the study. Acceptance from the Danish Data Protection Agency will be sought in a separate application for the biobank for future research. Before samples from the biobank for future research can be used, a study protocol will be submitted for approval by an Ethics Committee. Blood and urine samples and associated data from the research biobank and the biobank for future research belong to the study investigators.

13 Statistical methods and determination of sample size

13.1 Calculations

The average changes after week 12, 24 and 48 in primary and secondary outcomes will be calculated for each of the three groups. Results will be presented as means (SD) for normally distributed variables and as medians (inter-quartile range) for non-normally distributed variables.

13.2 Statistical methods

Intention-to-treat (ITT) analysis will be performed as the primary analysis on all primary and secondary outcomes after the last participant has participated in the last visit. Missing values will be handled with a last observation carried forward approach for ITT analysis. Per-protocol (PP) analysis will only be performed in case of sensitivity testing.

Parametric tests (general linear models) will be used to test differences in outcomes from baseline to follow-up. Heterogeneity in responsiveness to the interventions will be tested by dividing each intervention group into smaller groups based on data distribution (medians) or clinically meaningful cut-points. If model assumptions cannot be met even after logarithmic transformation, non-parametric tests will be used. Plots of residuals versus predicted values will be used to judge normality. Metabolic patterns will be tested with multivariate statistics. Adjustment for relevant confounders will be performed. Two-sided tests will be used. *P* values of <0.05 are considered significant. The statistical programs SPSS and SAS will be used for data analysis.

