10.1 Clinical Examination

Body weight will be measured at visit V1 (baseline), V5 (week 24) and V6 (week 48) in a fasting condition and at V4 (week 12) in a non-fasting condition. Height will only be measured and recorded at V1. Blood pressure, waist and hip circumference will be performed at visits V1, V5 and V6 in a fasting condition. Procedures will be conducted after appropriated training of study personnel involved in carrying out the procedures.

Body weight will be measured with the participant wearing light indoor clothes and no shoes at the same calibrated scale after emptying the bladder. Two measurements are made and both are noted to the nearest 0.1 kg. The average of the two measurements is used in further analysis.

Height is measured using a wall-mounted stadiometer with the participants not wearing shoes and with the heels, buttocks and upper part of the back remaining in contact with the wall/back of the stadiometer. Two measurements are made and both results are noted to the nearest 0.1 cm. The average of the two measurements is used in further analysis.

Waist circumference is measured halfway between the lowest point of the costal margin and highest point of the iliac crest at the end of expiration with the participant in a standing position. All anthropometric measurements are performed twice with the average of the two measurements used in further analysis.

Hip circumference is measured at the level of the greater femoral trochanter; both are measured to the nearest 0.5 cm at the end of expiration with the participant in a standing position. All anthropometric measurements are performed twice with the average of the two measurements used in further analysis.

Blood pressure is measured with the participant in sitting position after minimum 10 min of rest, not talking during the measurement. Blood pressure measurements are repeated three times separated by two min breaks. Mean values are calculated.

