### Hypotheses for the primary outcomes:

1. We hypothesize that ACC is superior compared with usual dietary care (the control group) in reducing HbA1c or MAGE from baseline to end-of-treatment at week 24 (from V1 to V2).

Superiority is claimed if:

- a. the 95% confidence interval for the estimated difference in change between the groups for HbA1c or MAGE, estimated using a baseline corrected linear mixed model, excludes 0 and the P-value is <0.05: and,
- b. the estimated difference in HbA1c or MAGE between the two groups is equal to/surpass the minimal important difference in favour of the ACC group.

2. We hypothesize that BCC is superior compared with usual dietary care (control group) in reducing HbA1c or MAGE from baseline to end-of-treatment at week 24 (from V1 to V2).

Superiority is claimed if:

- c. the 95% confidence interval for the estimated difference in change between the groups for HbA1c or MAGE, estimated using a baseline corrected linear mixed model, excludes 0 and the P-value is <0.05: and,
- d. the estimated difference in HbA1c or MAGE between the two groups is equal to/surpass the minimal important difference in favour of the BCC group.

3. We hypothesize that BCC is equivalent to ACC in reducing HbA1c or MAGE from baseline to end-of-treatment at week 24 (from V1 to V2).

Equivalence is claimed if:

- e. The 90% confidence interval for the estimated difference in change between the groups for HbA1c or MAGE does not surpass minimal important difference in a negative or positive direction (16).

Hypotheses for the secondary outcomes can be found in the study protocol and [clinicaltrials.gov](https://clinicaltrials.gov).

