### Timing of outcome assessments

HbA1c was measured at the screening visit (V0), at the baseline visit (V1), after 12 weeks of intervention, after 24 weeks (V2) of intervention, and after six months follow-up (V3). MAGE was measured after the baseline visit (V1), and after 24 weeks of intervention (after V2).

See section 6: Analyses for timing of secondary/descriptive/explorative outcome assessments.

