## Analysis methods

Analyses of the primary outcomes will be performed based on efficacy estimates.

Before further analysis and before unblinding, all variables will be inspected to detect outliers to uncover potential errors, such as registration errors.

All continuous outcomes covered by this SAP will as a rule be modelled using baseline corrected repeated measures regression (22) with the following fixed effects and interactions between fixed effects: Visit, Visit (factorial)\*Treatment. Data from V1, V2, and V3 will be included in the analysis. The models will be specified with a restricted maximum likelihood estimation method and a repeat on participant level (unstructured covariance structure). Model fit will be evaluated using graphical methods before estimating the treatment effects and if necessary, outcomes will be log-transformed. Estimated mean differences (CI95%) between groups (CI95%), conditional means (CI95%), and within group changes (CI95%) will be extracted from the model. For log-transformed outcomes the results will be back-transformed and be presented as the ratio between estimated mean differences (CI95%), estimated conditional geometric means (CI95%) and relative changes within groups (CI95%), respectively. If log-transformation cannot meet distribution assumptions, a generalized mixed linear model with an appropriate distribution will be applied instead of the repeated measures regression model. In case the distribution does not comply with the distributions available in the generalized mixed linear model a non-parametric test will be used to compare the change scores for the given outcome.

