## Missing data

The number/frequency of missing values for the primary outcomes in each group at each time point will be provided. In the primary analysis, missing data are handled implicitly by maximum likelihood estimation in the linear mixed model and missing data will be assumed to be missing at random. This is equivalent to making multiple imputations for each treatment group separately and estimating the treatment effect that would have been found had all subject completed their assigned treatment (efficacy estimate) under the missing at random assumption.

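### The SAP never withdraws the protocol's last-observation-carried-forward rule, which is therefore the only stated missing-data rule for outcomes and a fallback test that the SAP's mixed model does not reach

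*Protocol*

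**What the plan says.** Protocol 13.2 makes intention-to-treat the primary analysis for every primary and secondary outcome, using general linear models, and adds: "Missing values will be handled with a last observation carried forward approach for ITT analysis". No outcome is exempted.

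The SAP (Analysis methods) instead plans a baseline-corrected repeated-measures model for the continuous outcomes it covers, fitted by restricted maximum likelihood with an unstructured covariance. On visits it says: "Data from V1, V2, and V3 will be included in the analysis". In the SAP's numbering these are baseline, week 24 and week 48, so week 12 is left out. Under Missing data it says: "In the primary analysis, missing data are handled implicitly by maximum likelihood estimation in the linear mixed model", with missingness assumed to be at random.

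If neither log-transformation nor a generalised mixed model fits, "a non-parametric test will be used to compare the change scores for the given outcome". The SAP does not say what change score a participant without a V2 or V3 value receives.

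The SAP does not mention LOCF, either to keep it or to replace it.

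**The concern.** Two different rules are on record for the same intention-to-treat analysis, and neither document reconciles them. Where the SAP's model does not reach, the protocol's rule is the only one an analyst can point to, and it suits this visit schedule poorly. An outcome measured only at baseline and week 24 has nothing to carry forward but baseline, so each drop-out enters as an observed change of exactly zero. With similar drop-out in the arms, this shrinks the contrast and understates its standard error. A rule that compares an estimate or an interval with a fixed minimal important difference (MID) is sensitive to both.

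**Working it through.** **Step 1: which rule reaches which analysis**

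| Outcome or analysis | Protocol | SAP | Rule stated |
|---|---|---|---|
| HbA1c and MAGE, week 24 | Primary (9.1.1) | Primary, mixed model | SAP model; LOCF not withdrawn |
| DXA body composition | Secondary (9.1.2), measured at V1 and V5 (10.5) | Named in Objectives, in no outcome list | LOCF only |
| Free fatty acids | Secondary (9.1.2); not among the assays in 10.2 or Table 4 | Not listed | LOCF only |
| HbA1c, week 12 | Secondary (9.1.2), measured at V4 (10.2) | Noted under timing; not in the model; secondary list has HbA1c for V3 only | LOCF only |
| Non-parametric test | Foreseen (13.2) | Change scores, missing values not addressed | LOCF only |

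For DXA at week 24 and HbA1c at week 12, the last earlier value is baseline, so LOCF means zero change. If body weight reached the fallback, LOCF could carry a value taken "at V4 (week 12) in a non-fasting condition" into a fasting week-24 endpoint.

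**Step 2: the protocol's own sample size**

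Inputs (protocol 13.3): difference 3.5 mmol/mol, SD 7, two-sided 5%, 80% power. The MAGE inputs, 0.35 and 0.7 mmol/l, have the same ratio. The normal approximation gives n = 2 × (1.960 + 0.842)² × (7/3.5)² = 62.8, so 63 per arm; the t-test gives 64, as stated. Then 3 × 64 = 192 and 192 × 1.2 = 230.4, matching Table 5. Enrolment is 77 per arm.

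**Step 3: size of the effect if LOCF were applied to MAGE**

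Assumptions: drop-out fraction d, equal in both arms and unrelated to outcome; baseline carried forward; SD of change 0.7; true difference 0.35; MID 0.35 (SAP, Outcome definitions).

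- Expected contrast: (1 − d) × 0.35. At d = 0.2 this is 0.28.
- Variance of change in an arm with mean change μ: (1 − d) × 0.49 + d(1 − d) × μ². At d = 0.2 this is 0.392 for μ = 0 and 0.392 + 0.16 × 0.1225 = 0.4116 for μ = 0.35.
- LOCF standard error: √[(0.392 + 0.4116)/77] = 0.102. An unbiased MAR analysis has 77 × 0.8 = 61.6 observed per arm and standard error √(2 × 0.49/61.6) = 0.126.
- Superiority rule (significant, and estimate at least 0.35): an estimate of 0.35 is already significant, so the MID condition decides. LOCF: 1 − Φ((0.35 − 0.28)/0.102) = 25%. MAR: 50%. A simulation of 15,000 trials gave 24.2% and 49.9%.
- False equivalence when the true difference equals the margin: Φ((0.35 − 0.28)/0.102 − 1.645) = 17%. It is 16% if both arms also share a 0.35 improvement. MAR: 5%. Simulation gave 16–17%.

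| d | LOCF contrast (mmol/l) | Superiority rule met | False equivalence |
|---|---|---|---|
| 10% | 0.315 | 37% | 9% |
| 20% | 0.28 | 25% | 16–17% |
| 30% | 0.245 | 14% | 27–29% |
| MAR, any d | 0.35 | 50% | 5% |

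Power for p < 0.05 alone hardly moves: 78% with LOCF and 79% with MAR at d = 0.2.

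**Step 4: HbA1c and unequal drop-out**

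A week-12 HbA1c exists, so baseline is carried only for those lost before it. With 20% drop-out, if half of the drop-outs have a week-12 value showing the full effect (assumed), the contrast is 3.15 mmol/mol and false equivalence 9%. If all do, the figures are 3.5 and 5%.

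For unequal drop-out, assume baseline carried forward and true HbA1c changes of −3.5 (BCC) and −7.0 (ACC). BCC 30% and ACC 10% gives 0.9 × 7.0 − 0.7 × 3.5 = 3.85 and false equivalence 2.4%. Reversing the rates gives 0.7 × 7.0 − 0.9 × 3.5 = 1.75 and 49%.

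**The case against.** The strongest reply is that the SAP has already replaced LOCF in substance. It is the later document, and it also changes the model and the software given in 13.2. Where it keeps protocol content it says so, for sample size and for the secondary hypotheses. It makes no such reference for missing data. This stands for every outcome the SAP covers: there the defect is an undocumented change, not two live rules.

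A reader might infer from Step 3 that the planned BCC–ACC equivalence test is too easy to pass. The documents do not support that. The criterion "The 90% confidence interval for the estimated difference in change between the groups for HbA1c or MAGE does not surpass minimal important difference" appears only in the SAP, as does the MID condition for superiority, and the SAP's method for those outcomes is the MAR mixed model. The protocol hypothesises no difference between BCC and ABC-ACC but sets no margin and no equivalence test. Neither document pairs LOCF with equivalence. Under the protocol's own criterion, p < 0.05, the loss of power is about one percentage point.

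Three further limits also stand:

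- 20% carried forward is a high figure. The SAP excludes participants lost before baseline, and protocol 9.5.3 plans follow-up of those who withdraw, with their permission.
- The fallback is reached only after two other approaches fail. The Step 3 figures are for means and would not transfer exactly to a rank test.
- The omitted outcomes are not primary and carry no equivalence claim, so those figures do not apply to them.

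The reply does not cover the omitted outcomes or the fallback. There the SAP states no rule that could supersede LOCF.

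**Conclusion.** The concern holds in a limited form. LOCF was not withdrawn, and it is the only stated rule for DXA body composition, free fatty acids, week-12 HbA1c and the non-parametric change-score comparison. Wherever baseline is the last value, it sets a drop-out's change to zero. The week-24 HbA1c and MAGE analyses, including equivalence, should be read as using the SAP's mixed model and are not biased by LOCF as planned.

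The MAGE figures show what would follow if the protocol's rule were applied to the SAP's decision rules. They rest on equal, outcome-independent drop-out, a common SD of change, and no precision gained from baseline or later visits. It would also be wrong to say that LOCF always favours equivalence: the direction depends on which arm loses more participants. This is worth settling before analysis, because the remaining rule is biased and cheap to replace.

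**What to change.** In the SAP's Missing data section:

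1. State that the MAR mixed model replaces the protocol's LOCF for all continuous outcomes, with a one-line reason.
2. Extend the model to the protocol outcomes the SAP omits, and add the week-12 visit to the HbA1c model. That visit also brings in information on participants lost between weeks 12 and 24.
3. Where the non-parametric fallback is used, handle missing V2 or V3 values by multiple imputation within treatment group, and say how the test is pooled over imputations. This agrees with the SAP's own description of its model as equivalent to imputing each group separately.

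The cost is a few sentences, a little more analysis work, and a note recording the departure from protocol 13.2. Making the change in the SAP avoids a retrospective protocol amendment, which would need a favourable ethics opinion under 15.5 if judged substantial. The SAP says analysis begins once it has been uploaded, so the change should be made before then.
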